9.2.3 Observation Period

Each patient will be followed from the date of first dose of cladribine tablets until loss to follow-up, withdrawal of consent, death or the end of the data collection period, whichever comes first. Patients will be followed for 24 months from first dose and up to 30 months for those patients who may require a delay of initiation of Year 2 treatment for up to 6 months due to low lymphocyte counts. Follow-up will continue regardless of cladribine tablets discontinuation.

9.2.4 Frequency of Assessments

Table 1 lists the Schedule of Assessments. Patients are considered enrolled once the informed consent form (ICF) has been signed prior to any data collection for this study. The Baseline Visit is the visit immediately prior to the patient initiating treatment with cladribine tablets. If the sites anticipate a delay between the decision to start cladribine tablets (i.e. prescription) and patient access to cladribine tablets (i.e. due to delays in cladribine tablets availability or access), the site can perform a Screening Visit first to determine eligibility of the patient and a subsequent Baseline Visit closer to the time the patient starts taking cladribine tablets. Data entered during the Baseline Visit are considered baseline data for the purposes of analysis.

Sites are asked to enter patient follow-up data for up to 24 months after a patient received initial dose if Year 2 treatment course is not delayed and up to 30 months after initial dose if Year-2 treatment course is delayed up to 6 months. Visits will be conducted within the context of routine clinical care; thus, the timing of study visits is approximate and not mandated by the study protocol.

It is anticipated that patients enrolled in the study may not immediately start cladribine tablets after the decision to initiate cladribine tablets is made, owing to the need to first discontinue their current injectable DMD (for a time period determined by the investigator) and to potential delays in obtaining cladribine tablets in the clinical setting. The initial PRO only collection (Month 1) is intended to be obtained after the patient has started treatment with cladribine tablets. The timing of Visit 1 (Month 2) and the subsequent visits may need to be adjusted based upon the actual start date of cladribine tablets, which will be recorded by the investigator.

In accordance with the USPI, it is anticipated that patients may not receive their second course of cladribine tablets precisely 12 months after the initiation of cladribine tablets owing to ALC levels <800 cells per microliter or other potential clinical factors. In the event that the second course of cladribine tablets is delayed beyond Month 13, the PRO only collection scheduled for Month 13 should be adjusted to occur during the start of the second course of cladribine tablets. The timing of Visit 4 (Month 14) and the subsequent visits may need to be adjusted based upon the actual start date of the second course of cladribine tablets, which will be recorded by the investigator.

Table 1. Schedule of Assessments

| | Data Collection Time Points (As Expected Based on Routine Clinical Practice) | | | | | | | | | |
|---|--|---|--|-------------------------------|-------------------------------|--------------------------------|---|--------------------------------|--|--|
| Assessments | Pre-baseline Screening Visit (Days -45 to 0) | Baseline Visit ^a (Baseline) Month 0 | PRO Only ^b Month 1 | Visit #1 Month 2 | Visit #2 Month 6 | Visit #3 Month 12 | PRO Only ^b Month 13 | Visit #4 Month 14 | Visit #5 Month 18 | Visit #6 Month 24 |
| Informed consent | Х | | | | | | | | | |
| Medical history, previous relapses, previous DMD treatment | | Х | | | | | | | | |
| Inclusion / exclusion criteria | Х | | | | | | | | | |
| Demographic data | Х | | | | | | | | | |
| Pregnancy test, HIV, hepatitis B, hepatitis C and tuberculosis status | | Х | | | | Х | | | | |
| Cladribine tablets ^c | | Х | | Х | | Х | | Х | | |
| Other MS DMD during study period, if applicable | | | | Х | | Х | | Х | | Х |
| Neurological examination as per standard of care | | Х | | | Х | Х | | | Х | Х |
| Physical examination as per standard of care | | Х | | | | | | | | |
| Relapse count (prospective) ^d | | | | | | Х | | | | Х |
| MRI documentation ^e | | Х | | | Х | Х | | | Х | Х |
| Hematology assessment (ALC, CBC, lymphocyte subsets) $^{\rm f}$ | | Х | | Х | Х | Х | | Х | Х | Х |
| Patient-reported outcomes | | | | | | | | | | |
| Treatment adherence ^g | | X ^h | Х | Х | | | Х | Х | | |
| TSQM | | X ^h | | | Х | Х | | | | Х |
| SF-36 | | X ^h | | | X | Х | | | | Х |
| MFIS-5 | | X ^h | | | Х | Х | | | | Х |
| BDI-FS | | X ^h | | | Х | Х | | | | Х |
| WPAI-MS | | X ^h | | | Х | Х | | | | Х |
| PDDS | | X ^h | | | Х | Х | | | | Х |
| Adverse events ⁱ | | Х | | Х | Х | Х | | Х | Х | Х |

| | Data Collection Time Points (As Expected Based on Routine Clinical Practice) | | | | | | | | | |
|-------------|--|---|--|-------------------------------|-------------------------------|--------------------------------|---|--------------------------------|--|--|
| Assessments | Pre-baseline Screening Visit (Days -45 to 0) | Baseline Visit ^a (Baseline) Month 0 | PRO Only ^b Month 1 | Visit #1 Month 2 | Visit #2 Month 6 | Visit #3 Month 12 | PRO Only ^b Month 13 | Visit #4 Month 14 | Visit #5 Month 18 | Visit #6 Month 24 |
| pci | | | | | | | | | | |

^a Duration between end of previous treatment and start of cladribine tablets is at the discretion of the investigator.

^b At the PRO only time point, patients fill out the PROs at their home; patients do not come to the clinic for filling out PROs at these time points.

^c Cladribine tablets are expected to be taken according to the USPI. If cladribine tablets are discontinued, reasons for discontinuation and follow-up MS treatment will be collected.

^d Relapse count includes relapses associated with hospitalization and/or glucocorticoid use.

^e For baseline MRI documentation sites are asked to record patients' most recent MRI results prior to starting cladribine tablets, which is expected to have been taken within the prior 90 days. During follow-up MRI scans are collected as available per routine practice. MRI documentation collected at baseline and follow-up are assessed by a central neuroradiology center. Specific instructions for transfer of the MRIs to the central neuroradiology center will be provided in a separate manual.

^f Investigators are expected to assess patients' ALC in accordance with the USPI, that is, before initiating cladribine tablets in Year 1, before initiating cladribine tablets in Year 2, and 2 and 6 months after start of treatment in each treatment year or as clinically indicated. It is assumed that investigators will not exclusively assess the ALC, but rather the CBC and, at some of these time points, also lymphocyte subsets. These data will be reported as available from routine practice. If the investigator assesses JCV status, these data should be recorded as well.

^g Treatment adherence questions, based on modified versions of the MS-TAQ, will be completed by patients via ePRO: at Baseline Visit (modified for self-injectables to assess adherence during last previous injectable DMD treatment) as well as at the end of Month 1, Month 2, Month 13, and Month 14 (modified for cladribine tablets).

^h Baseline PRO scales will be completed before first cladribine tablet dose is taken.

ⁱ Adverse events, **C**, relapse count, and PDDS scores will be collected as per running page and will be recorded on an ongoing basis as new information is collected for up to 24 months (or 30 months if Year 2 treatment is delayed).

^j If Year 2 treatment is delayed, final follow-up visit may occur at Month 30.

Abbreviations: ALC=absolute lymphocyte count, BDI-FS=Beck-Depression Inventory-Fast Screen, CBC=complete blood count, DMD=disease-modifying drug, ePRO = electronic Patient-Reported Outcome, HIV=human immunodeficiency virus, JCV=John Cunningham Virus, MFIS-5=Modified Fatigue Impact Scale – 5-item version, MRI=magnetic resonance imaging, MS=multiple sclerosis, MS-TAQ=Multiple Sclerosis Treatment Adherence Questionnaire, PDDS=Patient Determined Disease Steps, PRO=Patient-Reported Outcome, SF36=36-Item Short Form Health Survey; TSQM=14-Item Treatment Satisfaction Questionnaire for Medication, USPI=US Prescribing Information, WPAI-MS=Work Productivity Activity Impairment – MS.

9.2.5 Withdrawal from the Study

Patients may discontinue from the study at any time. Investigators may choose to discontinue patients from the study at any time. Further, enrolled patients who do not take at least 1 dose of cladribine tablets will be withdrawn from the study. The reason for any study discontinuations will be collected, if available.

9.3 Variables

The following variables will be collected:

Screening and/or Baseline Visit

- Patient demographics, including: age, sex, weight, self-reported race/ethnicity
- Date of diagnosis of MS, date of first symptoms of MS
- DMD treatments received prior to study enrollment, since MS diagnosis (including medication doses and routes of administration, start dates, stop dates, and reasons for discontinuation)
- Relapse of MS in the 2 years prior to the study period or since MS diagnosis, if diagnosis <24 months (including dates of onset and resolution of relapse)
- Most recent MRI results prior to starting cladribine tablets (baseline MRI), which is expected to have been taken within the prior 90 days (number of T1 Gd+ lesions; number of new T2 lesions compared to most recent prior MRI; number of newly enlarging T2 lesions compared to most recent prior MRI; number of CU lesions; presence of brain atrophy and segmental atrophy)
- Results of MRI in the 2 years prior to study enrollment or since MS diagnosis, if diagnosis <24 months (including prior documentation of number of T1 Gd+ lesions; new or newly enlarging T2 lesions; number of CU lesions; presence of brain atrophy and segmental atrophy)
- Results of neurological examination as per standard of care (e.g., Kurtzke Functional System Scores (FSS), ambulation up to 500 meters and Expanded Disability Status Score [EDSS])
- Results of physical examination as per standard of care
- Hematology assessment (white blood cell count, hemoglobin, hematocrit, platelet count, ALC). If the investigator assesses JCV status, these data should be recorded as well
- Pregnancy, human immunodeficiency virus (HIV), hepatitis B, hepatitis C and tuberculosis test results
- ePRO assessments (treatment adherence questions based on modified versions of the MS-TAQ, TSQM, SF-36, MFIS-5, BDI-FS, WPAI-MS, PDDS)
- Comorbid conditions
- List of all MS symptomatic specific medications taken in the 2 years prior to study enrollment (or since MS diagnosis, if diagnosis <24 months), including medication start and stop dates and reasons for discontinuation

Follow-Up Visits

The anticipated timing of assessments is presented in Table 1: Schedule of Assessments.

- Medication log of cladribine tablets treatment during the study period, including medication start dates, medication stop dates, medication dose (mg), number of dose and reasons for discontinuation
- Medication log containing other MS DMD treatments (if applicable) during the study period, including medication doses and routes of administration, start dates, stop dates and reasons for discontinuation
- Relapse of MS during the study period as determined by the investigator (see Section 9.1.2.1 for a guide on definition) including date of onset, resolution of relapse and definition for relapse used
- Relapse of MS associated with hospitalization (relapse as primary diagnosis or reason for hospitalization) during the study period as determined by the investigator (see Section 9.1.2.1 for a guide on definition) including date of onset, resolution of relapse and definition for relapse used
- Relapse of MS associated with glucocorticoid use during the study period as determined by the investigator (see Section 9.1.2.1 for a guide on definition) including date of onset, resolution of relapse and definition for relapse used
- MRI scans from all MRIs performed during the study period; MRI scans are assessed by a central neuroradiology center; data includes:
- Results of neurological examination as per standard of care (Kurtzke FSS, ambulation up to 5000 meters and EDSS)
- Hematology assessment (white blood cell count, hemoglobin, hematocrit, platelet count, ALC). If the investigator assesses JCV status, these data should be recorded as well
- Pregnancy, HIV, hepatitis B, hepatitis C and tuberculosis test results
- Comorbid conditions

- AEs as a continuous log
- ePRO assessments (treatment adherence questions based on modified versions of the MS-TAQ, TSQM, SF-36, MFIS-5, BDI-FS, WPAI-MS, PDDS)

[figure not shown]
Derived and transformed data needed for the analysis are described in Section 9.7.2.

9.4 Data Source

Data sources for this study will include data extracts from patients' medical records performed by site personnel as well as questionnaires directly filled out by patients. The data to be collected in the study will be obtained by means of an Electronic Data Capture (EDC) system. The data in the electronic Case Report Form (eCRF) should be consistent with the relevant source documents. Further details are provided in Section 9.6.

Each patient will be able to be identified from their patient file. Additionally, any other documents containing source data must be filed (e.g., laboratory value listings, etc.). Such documents must bear at least the patient number and the date when the procedure was performed. Information should be printed by the instrument used to perform the assessment or measurement, if possible. Information that cannot be printed by an automated instrument will be entered manually. Medical evaluation of such records should be documented as necessary and the documentation signed and dated by the investigator.

Patient questionnaire data will be recorded directly via EDC rather than entered into the patient's original medical file. In such cases there will be no record in the original patient file (either on paper or electronically) that corresponds to the entries. For all PROs, the patient will enter data directly with a validated ePRO.

9.6 Data Management

The main purpose of the eCRF is to obtain data required by the non-interventional study protocol in a complete, accurate, legible and timely manner. The data in the eCRF should be consistent with the relevant source documents.

The investigator or designee is responsible for ensuring that the data collected in the course of this study is accurate and documented appropriately on all applicable forms. Data will then be processed, evaluated, and stored in anonymous form in accordance with applicable data protection regulations. The investigator must ensure that the eCRFs and any other associated documents forwarded to the Sponsor or its designated organization contain no mention of any patient names.

The data will be entered into a validated database. The Contract Research Organization (CRO) will be responsible for data processing, in accordance with the CRO's data management procedures. Database lock will occur once Quality Control and Quality Assurance procedures (including reconciliation of SAEs, ADRs, AESIs and special situations) and coding activities have been completed. PDF files of the eCRFs will be provided to the investigators at the completion of the study.

9.7 Data Analysis

Further details will be provided in a Statistical Analysis Plan.

There will be a baseline analysis and 3 interim analyses: The baseline analysis will summarize baseline characteristics. In the first interim analysis, mainly for safety purposes, safety, adherence and PRO data will be analyzed for the subset of the first 30 patients enrolled into the study at the 6-month time point. A second interim analysis on the safety, adherence and PRO data will be performed as soon as 6-month data are available for all patients. The third and full interim analysis will be performed on the 12-month data. The final analysis evaluating the primary and secondary objectives will be on the 24-month data at the end of the study.

All patients enrolled in the study who receive at least 1 dose of cladribine tablets will be included in the analyses. The primary endpoint will be analyzed at Month 24. All secondary endpoints on relapse rates, PROs, MRI, and treatment patterns will be analyzed at Month 12 (12-month interim analysis) and Month 24 (final analysis). PRO data will additionally be analyzed once the first 30 patients reach the 6-month follow-up as well as at Month 6 for all enrolled patients. Safety data will also be assessed at Month 6 for the first 30 patients enrolled as well as at Months 12 and 24, unless Year 2 treatment is delayed in which case the final safety assessment would occur at Month 30.

9.7.1 Analysis Sets

Full Analysis Set

The Full Analysis Set includes all patients enrolled in the study who received at least 1 dose of cladribine tablets.

Per Protocol Analysis Set

The Per Protocol Population includes all patients who have completed a full treatment course of cladribine tablets (2 weeks of treatment (4-5 doses per week) for years 1 and 2), according to the USPI and are compliant with all entry criteria.

Safety Analysis Set

The Safety Population includes all patients enrolled in the study who have received at least 1 dose of cladribine tablets (same as Full Analysis Set).

9.7.2 Derived and Transformed Data

Data will be transformed if required by the analysis method, e.g. to approximate the normal distribution of the data. Details on the eventual derivation/transformation of the analysis variables will be given in the Statistical Analysis Plan. For the primary outcome, the patterns of missingness will be explored. When the number of missing values is substantial (>5%), multiple imputation methodology will be considered for the analysis of the primary objective.

9.7.3 Statistical Methods

Descriptive statistics will be used to summarize data. If the outcome in question is a continuous variable, the number of observations, number of missing values, mean, SD, median, first quartile and third quartile, minimum and maximum values will be presented; if the outcome is categorical, numbers and percentages of patients for each of the categories and numbers and percentages of missing values will be presented.

Where appropriate, 95% CIs will be presented. For continuous data, CIs for the mean will be calculated assuming a normal distribution of the data. CIs for binary endpoints will be presented using the Clopper-Pearson method.

Time to event data will be analyzed both descriptively as continuous data and through Kaplan-Meier analysis.

Primary Endpoint Analysis:

The ARR over the 24-month period will be presented, accompanied by the respective 95% CI.

Sensitivity analyses of the ARR will be performed considering the relapses as count data and using a negative binomial regression model with time as explanatory variables. A zero-inflated negative binomial regression model will be also considered.

Secondary Endpoints Analysis:

All secondary endpoints will be analyzed at Month 12 (interim analysis) and Month 24 (final analysis). Data will be summarized descriptively.

ARR (prospective assessment): The ARR over the 12-Month and 24-Month follow-up period after starting cladribine tablets will be presented, accompanied by the respective 95% CIs.

Other relapse analyses: The proportion of patients experiencing a relapse, ARR associated with hospitalization and associated with glucocorticoid use will be presented together with the corresponding 95% CI over the 24-month and over the 12-month period.

[figure not shown]
Treatment adherence: Treatment adherence, based on modified versions of the MS-TAQ, will be described at baseline (modified for self-injectables to assess adherence during last previous

injectable DMD treatment), and for the first and second course of treatment with cladribine tablets during the first and second treatment year (modified for cladribine tablets).

Other PROs: For each ePRO score (TSQM-14, SF-36, MFIS-5, BDI-7, WPAI-MS, and PDDS), Resolution and the actual value at each visit and change in scores from baseline to Month 6, 12 and 24 will be described.

Treatment patterns: Prior treatment patterns will be described at baseline (previous DMD treatment(s) and baseline characteristics of patients initiating cladribine tablets). Treatment discontinuation of cladribine tablets and the reasons for discontinuation will be described, as will be the follow-up treatments.

Annualized Relapse Rate (retrospective assessment): The ARR during the last 24 months before starting cladribine tablets (or since MS diagnosis, if diagnosis <24 months) will be presented. accompanied by the respective 95% CIs.

Safety: All safety data (AEs and hematology data, including lymphocyte subtype data, as available) will be evaluated descriptively.

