Other relapse analyses	Proportion of patients experiencing a relapse (24-month and 12-month periods) and ARR over the 12-month period	24-month treatment period (or 30 months if Year 2 treatment is delayed) and 12-month	Section 14.2
	Proportion of patients with relapse associated with hospitalization and ARR associated with hospitalization		
	Proportion of patients with relapse associated with glucocorticoid use and ARR associated with glucocorticoid use	from first dose of cladribine tablets	
To assess treatment patterns (Multiple Sclerosis [MS] treatment prior to transition to cladribine tablets, since MS diagnosis, concomitant treatment for MS during the last 2 years prior to initiation of cladribine tablets (or since MS diagnosis if diagnosis <24 months), follow-up treatment in case of discontinuation of cladribine tablets)	
 
Assessment of previous treatment for MS:         
 
Previous DMD received for MS during the last 2 years
 
Number of previous DMD received for MS (a) during the last 2 years and (b) in total
 
Reasons for discontinuation of last previous DMD
 
 
 
Assessment of concomitant MS medications used during the study period
 
Proportion of patients who discontinue cladribine tablets         
 
Reason for discontinuation of cladribine tablets
 
Elapsed time to discontinuation after the first dose of cladribine tablets
 
Number of doses and % of planned doses of cladribine tablets aproduct Information [USPI]) received
 
 
 
Subsequent treatment chosen following discontinuation of cladribine tablets
 
	For previous treatment: 24- month period prior to initiation of cladribine tablets For concomitant medication, cladribine tablets discontinuation and subsequent treatment: 24- month period from first dose of cladribine tablets (or 30 months if Year 2 treatment is delayed)	Section 11.3 and section 12
To estimate the ARR over the 24-month period prior to initiation of cladribine tablets (or since MS diagnosis if diagnosis <24 months)	The ARR based on the last 24 months prior to the start of treatment with cladribine tablets (or since MS diagnosis if diagnosis <24 months) (retrospective data)	24-month period prior to initiation of cladribine tablets (or since MS diagnosis if diagnosis <24 months)	Section 11.3

Objectives	Endpoints (Outcome Measures)	Endpoints (Outcome Measures) Timeframe	IAP section

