#### Significance level

When confidence intervals (CIs) are to be calculated, these will be two-sided with a confidence probability of 95%, unless otherwise specified in this IAP. For continuous data, CIs for the mean will be calculated assuming a normal distribution of the data. CIs for binary endpoints will be presented using the Clopper-Pearson method. All statistical tests mentioned in this IAP are to be regarded as exploratory. The significance level is 5% two-sided. If p-values are to be presented for descriptive purposes it will be indicated with the statement that no inferential conclusion should be drawn from the p-value.

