#### Presentation of continuous and qualitative variables

Continuous variables will be summarized using descriptive statistics, i.e.

- number of patients, number of patients with non-missing values, numbers of patients with missing values,
- mean, standard deviation (SD),
- median, 25th Percentile-75th Percentile (Q1-Q3),
- minimum, and maximum.

If there are no missing values this will be indicated by a 0.

Qualitative variables will be summarized by counts and percentages.

Unless otherwise stated the calculation of proportions will be based on the number of patients of the analysis population of interest. Therefore, counts of missing observations will be included in the denominator and presented as a separate category.

In case the analysis refers only to certain visits, percentages will be based on the number of patients still present in the study at that visit, unless otherwise specified.

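### On the visible text, the 24-month proportion of patients with a relapse is a crude binomial share over unequal follow-up, so it does not estimate a 24-month risk, and the direction of its error is unknown

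*Protocol*

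**What the plan says.** Protocol 9.7.3, under other relapse analyses, says: "The proportion of patients experiencing a relapse, ARR associated with hospitalization and associated with glucocorticoid use will be presented together with the corresponding 95% CI". This is planned for both the 24-month and the 12-month period. In that sentence the hospitalization and glucocorticoid items are rates. Their proportions are listed as endpoints in Protocol 9.1.2.2 and again in SAP section 5, beside "Proportion of patients experiencing a relapse (24-month and 12-month periods".

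Four other places determine how the proportion would be computed:

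- **Interval.** SAP section 9, Significance level: "CIs for binary endpoints will be presented using the Clopper-Pearson method".
- **Denominator.** SAP section 9, Presentation of continuous and qualitative variables: "Unless otherwise stated the calculation of proportions will be based on the number of patients of the analysis population of interest". Missing values stay in: "counts of missing observations will be included in the denominator and presented as a separate category". The same paragraph allows a second rule: where an analysis refers only to certain visits, the denominator is the patients still in the study at that visit.
- **Length of follow-up.** Protocol 9.2.3 ends follow-up at loss, withdrawal of consent or death, and otherwise: "Patients will be followed for 24 months from first dose and up to 30 months for those patients who may require a delay".
- **Endpoint window.** SAP section 5 gives these endpoints 24 months, extended to 30 when the Year 2 course is delayed, plus a 12-month period with no extension.

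SAP section 5 refers the reader to SAP 14.2 for the detail. That section is blacked out in the public text.

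**The concern.** A proportion with an exact binomial interval is easy to interpret when every patient is observed for the same time. Here they are not. A patient lost at Month 5 can contribute a relapse only from those five months but still counts as one full patient in the denominator. A patient whose Year 2 course is delayed can contribute a relapse from Month 25 to Month 30 to a figure headed 24 months. The extra time is not handed out at random, because it follows the treatment delay, for example after a low lymphocyte count.

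The plan deals with the same problem elsewhere. The primary ARR divides by each patient's time on study (SAP 14.1.1). The windows for the PROs other than PDDS and MS-TAQ are counted from Day 1 whatever the Year 2 delay (SAP section 9, Time window). Time to discontinuation of cladribine gets a Kaplan-Meier analysis with censoring (SAP section 13). Nothing visible gives the relapse proportion similar protection.

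At stake is how the any-relapse, hospitalization and glucocorticoid proportions may be read. A reader will take them as 24-month risks and may compare them with other cohorts on that basis.

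**Working it through.** The available text gives no expected relapse proportion, dropout rate, share of delayed patients or sample size, so there is no plan figure to reproduce. What follows is an illustration on stated assumptions.

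**Assumptions.** Constant relapse rate L per year. A share d is lost uniformly over 24 months, non-informatively. Of those remaining, a share q is followed to Month 30. Relapses seen before a patient leaves are counted. The denominator is the whole FAS.

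**Formulas.**
- Risk by time t: F(t) = 1 − exp(−L·t).
- Mean observed share among early leavers: G = 1 − (1 − exp(−2L)) / (2L).
- Crude share: d·G + (1 − d)·[(1 − q)·F(2) + q·F(2.5)].

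**With L = 0.15.**
- F(2) = 1 − exp(−0.30) = 0.2592. This is the target.
- F(2.5) = 1 − exp(−0.375) = 0.3127.
- G = 1 − 0.2592/0.30 = 0.1361.
- d = 20%, q = 0: 0.8 × 0.2592 + 0.2 × 0.1361 = 0.2346, or 23.5%, which is 2.5 points low.
- d = 20%, q = 15%: 0.8 × (0.85 × 0.2592 + 0.15 × 0.3127) + 0.2 × 0.1361 = 0.2410, or 24.1%, which is 1.8 points low.
- d = 35%, q = 0: 0.65 × 0.2592 + 0.35 × 0.1361 = 0.2161, or 21.6%, which is 4.3 points low.

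**Where the two errors cancel.** q = d·(F(2) − G) / [(1 − d)·(F(2.5) − F(2))]. At L = 0.15 and d = 10%: 0.1 × 0.1231 / (0.9 × 0.0535) = 0.26. At d = 20%: 0.2 × 0.1231 / (0.8 × 0.0535) = 0.58. Above these shares of delayed patients the crude figure overstates the risk.

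**Range.** Over L = 0.1 to 0.3, d = 0 to 30% and q = 0 to 30%, the crude share minus the 24-month risk runs from −6.1 to +2.3 points.

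**12-month share.** There is no 30-month extension here. With L = 0.15 and 10% lost uniformly by Month 12, F(1) = 0.1393 and the leavers' mean is 1 − 0.1393/0.15 = 0.0714. The crude share is 0.9 × 0.1393 + 0.1 × 0.0714 = 0.1325, against a risk of 13.9%.

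**Sensitivity to the counting rule.** SAP 14.1.1 sets second-year relapses to missing when the Visit 6 question is unanswered. If all leavers counted as missing yet stayed in the denominator, 20% loss would give 0.8 × 25.9% = 20.7%. If the visit-based denominator applied instead, early leavers would drop out of it. The downward error would then vanish under non-informative loss, leaving only the upward one.

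**Scale.** At an assumed N of 100, the Clopper-Pearson interval for 33/100 is 23.9% to 43.1%, about 19 points wide.

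**The case against.** The strongest objection is that SAP 14.2, which governs these analyses, cannot be read. Protocol 9.7.3 also has an omitted block directly after the quoted sentence. A Month 24 cut, a denominator rule or a time-to-first-relapse analysis could sit in either place. This stands, so the recommendation is conditional on it.

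The default denominator also applies only where nothing else is stated. Prospective relapse counts are scheduled at Months 12 and 24, so the visit-based rule might be meant. This stands too: the visible text does not settle which rule applies, and the same data could yield different figures.

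A reader might infer that the plan understates relapse risk. The documents do not support that for the 24-month share, because the 30-month windows push the other way and neither share is given. A reader might also infer that the Clopper-Pearson interval is invalid. That does not follow either: if follow-up varies at random between patients, the yes/no indicator is still Bernoulli and the interval covers the crude share. The fault lies in what the share estimates.

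Finally, exposure-adjusted results are already planned. The primary ARR uses time on study, ARRs are planned for hospitalization and glucocorticoid use, and ARR is reported separately for completers and dropouts. The shift is also small beside the interval width. Both points limit the importance of the issue, but neither makes the proportion a 24-month risk.

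**Conclusion.** The point holds in a limited form. On the visible text, the proportion with a relapse (any, hospitalization-associated, glucocorticoid-associated) is a crude share over follow-up that can end early or run to Month 30. With the whole-FAS denominator, the 24-month share carries two opposing errors whose net sign is unknown, while early loss can only lower the 12-month share. In the main illustration the 24-month error is 1.8 to 2.5 points on a risk of 25.9%. That size rests on an assumed constant rate, uniform non-informative loss and relapses before leaving being counted.

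The documents do not show that no censoring-adjusted analysis exists, since SAP 14.2 is hidden. The endpoint is secondary and descriptive, and the primary ARR is not affected. Priority is low to moderate.

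**What to change.** If SAP 14.2 already fixes the window and handles censoring, confirm it and no change is needed. Otherwise add to SAP 14.2:

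1. For every patient, count only relapses with onset within 12 and within 24 months of first dose, whatever the timing of the Year 2 course.
2. Report 1 minus the Kaplan-Meier estimate of time from first dose to first relapse onset, read at exactly Months 12 and 24, with its 95% CI. Censor at the last date on which relapse status is known, and define that date for patients without a Visit 6 answer.
3. Do the same for the first hospitalization-associated and the first glucocorticoid-associated relapse.
4. Keep the crude n/N as a description and state which denominator rule applies.
5. State the non-informative censoring assumption.

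The cost is SAP wording and a little more programming. Relapse onset dates are already collected (Protocol 9.3) and Kaplan-Meier is already a general method in Protocol 9.7.3 and SAP section 9. The downside is the censoring assumption, which the planned comparison of completers with dropouts can help to judge.
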